6.3.2.4 Suspected Unexpected Serious Adverse Reactions

The sponsor will promptly evaluate all suspected unexpected serious adverse reactions (SUSARs) against cumulative product experience to identify and expeditiously communicate possible new safety findings to investigators, IRBs/IECs, and applicable health authorities based on applicable legislation.

To determine reporting requirements for single SUSAR cases, the sponsor will assess the expectedness of these events using the Reference Safety Information section of the study drug investigator's brochure.

The sponsor will compare the severity of each SUSAR and the cumulative event frequency reported for the study with the severity and frequency reported in the applicable reference document.

6.3.2.5 Follow-Up of Adverse Events

All AEs must be reported in detail on the appropriate page in the eCRF and followed to resolution, until the investigator deems the event to be chronic or not clinically significant (NCS), or until the patient is considered stable. Adverse events that are ongoing at the time of the EOS visit are to be followed for 30 days or until resolution, until the investigator deems the no longer clinically significant (CS), or until the investigator considers the patient's condition stable.

6.3.3 Vital Sign Measurements

The following vital signs will be measured at screening and at Visit 9:

- Blood pressure (measured supine, systolic and diastolic [mm Hg])
- Pulse (beats per minute)
- Body temperature (°F)
- Height (cm) and body weight (kg). Height is to be measured at screening only.

Supine blood pressure, pulse, and body temperature (°F) will be recorded after the patient has been recumbent and at rest for at least 5 minutes.

6.3.4 Eligibility

Eligibility will be evaluated at screening (Visit 1) and post-operatively on Day –1 (Visit 2). Patients must meet all inclusion criterion and no exclusion criteria to be assigned study drug.

6.4 Safety Monitoring Committee

There will be no safety monitoring committee.

6.5 Pregnancy

Female patients of childbearing potential (defined in inclusion criterion 5 of Section 4.1.1) are required to use effective contraception throughout the study.

Acceptable methods of contraception for female patients include oral contraceptives, other hormonal contraceptives (vaginal products, skin patches, or implanted/injectable products), or mechanical products such as an intrauterine device or barrier methods (diaphragm, condoms, spermicides). Note: female patients who are actively practising abstinence or who have a partner that is sterile (eg, vasectomy) will be permitted to participate in the study without contraception use.

Pregnancy is not regarded as an AE unless there is a suspicion that an investigational product may have interfered with the effectiveness of a contraceptive medication. Any pregnancy that occurs during study participation must be reported using a clinical study pregnancy form. To ensure patient safety, each pregnancy must be reported to [REDACTED] sponsor within 2 weeks of learning of its occurrence. The pregnancy must be followed up to determine outcome (including spontaneous miscarriage, elective termination, normal birth, or congenital abnormality) and status of mother and child even if the patient was discontinued from the

study. Pregnancy complications and elective terminations for medical reasons must be reported as an AE or SAE. Spontaneous miscarriages and congenital abnormalities of the child must be reported as an SAE.

Any SAE occurring in association with a pregnancy, brought to the investigator's attention after study completion, and considered by the investigator as possibly related to the study treatment, must be promptly reported to [REDACTED] sponsor.

6.6 Laboratory Analyses

Routine laboratory analyses will be performed by a central laboratory and will include the following assessments:

- **Haematology:** haemoglobin, haematocrit, red blood cell count, white blood cell count with differential, mean corpuscular volume, mean corpuscular haemoglobin, mean corpuscular haemoglobin concentration, and absolute platelet count.
- **Clinical chemistry:** total protein, sodium, potassium, chloride, albumin, glucose, HbA1c, blood urea nitrogen, creatinine, bilirubin (total and direct), alkaline phosphatase, aspartate aminotransferase, alanine aminotransferase, γ -glutamyltransferase, lactate dehydrogenase.
- **Urinalysis:** pH, glucose, ketones, specific gravity, nitrite, protein, bilirubin, urobilinogen, and blood. Microscopic urinalysis will be performed if urinalysis results are abnormal.

Urine pregnancy testing will be performed for all patients of childbearing potential before descemtorhexis at Visit 2 and at Visit 10.

Urine screening for drugs of abuse (opiates, methadone, cocaine, amphetamines, barbiturates benzodiazepines) and alcohol will be performed by dipstick.

6.6.1 Future Genetic Testing

A 6-mL blood sample will be obtained at Visit 1 for archiving and future genetic testing (Section 2.3). The blood sample will be collected only at sites in countries where allowed by local regulations and where approved by the IRB/IEC and relevant regulatory authorities.

Results of genetic testing will not be reported to the patient, relatives, or attending physician, and they will not be recorded in the participant's medical record. The participant may withdraw consent for genetic testing at any time up to analysis, even after the samples have been obtained. In the event of withdrawal of consent, the bio-repository will be notified to pull and destroy the sample.

For all samples collected for genetic testing, precautions are to be taken to maintain confidentiality by de-identifying the sample to prevent the genetic data from being linked to the identity of the participant.

6.7 Sample Collections

Sample collection, processing, and shipping must be performed according to local laboratory requirements and consistent with detailed procedures described in the study manual.

The volume of blood sampled is planned to be less than 20 mL in a single day and less than 35 mL over the entire study.

7 Statistical and Analytical Plan

A study eye will be identified for each patient. Unless otherwise specified, efficacy will be summarised for the study eye only. Ocular safety summaries by eye will be presented separately for the study eye and the non-study eye. Baseline measurements are the last measurements taken during the screening period (before Visit 2).

7.1 Primary Efficacy Endpoint

The primary efficacy endpoint is the central corneal ECD at Week 12 as assessed by the [REDACTED]

7.2 Secondary Efficacy Endpoints

Secondary efficacy endpoints include:

- Central corneal thickness change from baseline to each subsequent visit
- Percent change of central corneal thickness from baseline to each subsequent visit
- Central corneal ECD at each visit
- Number and percentage of patients who achieve central corneal ECD of 700 cells/mm² or more at each visit
- Time to achieve central corneal ECD 700 cells/mm² or more
- Number and percentage of patients who achieve cornea clearance at each visit where corneal clearance is defined as patients achieving a cornea thickness less than or equal to baseline cornea thickness and who have no corneal oedema
 - Number and percentage of patients who achieve cornea thickness less than or equal to baseline cornea thickness
 - Number and percentage of patients who achieve no corneal oedema
- Time to cornea clearance

- Time to return of cornea thickness to less than or equal to baseline cornea thickness
- Time to no corneal oedema

7.3 Exploratory Endpoints

Exploratory endpoints include the following:

- BCVA (letters) by ETDRS change from [REDACTED] to [REDACTED]
- Time to achieve BCVA by ETDRS letter score [REDACTED]
- Number and percentage of patients who achieve [REDACTED] or more improvement (BCVA by ETDRS)
- [REDACTED] corneal ECD at [REDACTED]
- [REDACTED] corneal ECD change from [REDACTED] at [REDACTED]
- Percent change of [REDACTED] ECD from [REDACTED] at [REDACTED]
- Changes in [REDACTED] parameters from [REDACTED] [REDACTED]
- Contrast sensitivity change (log values) from [REDACTED] [REDACTED]
- [REDACTED] domain and total scores change from [REDACTED] [REDACTED]

7.4 Sample Size Calculations

A sample size of 20 patients in each group will be needed to detect a difference of [REDACTED] in the measurement in the corneal ECD at Week 12 between K-321 0.4% QID/BID and placebo groups with a power of [REDACTED] for Step 1 and a power of [REDACTED] for Step 2 using a Wilcoxon rank sum test with a 0.050 two-sided significance level with closed testing procedures. Sample size was calculated by simulation. For the simulation, based on the existing literature ([Borkar DS, et al. 2016](#), [Moloney G, et al. 2017](#), [Iovieno A, et al. 2017](#)), placebo was assumed to be distributed normally with [REDACTED]

and K-321 was assumed to be distributed normally with [REDACTED]. Proportion of unmeasurable value of Week 12 due to corneal oedema and proportion of [REDACTED] value of Week 12 due to the withdrawal were assumed to be about 10% and about 5%, respectively. Here, unmeasurable value of Week 12 due to corneal oedema were imputed as zero, and [REDACTED] value of Week 12 due to the withdrawal were imputed by the last-observation-carried-forward (LOCF) method.

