(compiled from multiple papers), 31 (65%) out of 47 cases eventually achieved a clear cornea, with healing taking place as early as 1 month after the procedure (Van den Bogerd et al 2018). If there was persistent oedema at 6 months, then it was unlikely to resolve. If corneal oedema did not clear, some patients' corneas cleared without residual stromal damage after DMEK performed as rescue therapy between 4 and 8.5 months after Descemet's membrane stripping (Van den Bogerd et al 2018). All keratoplasty procedures, including DMEK, are associated with risks of graft detachment, graft failure or immune rejection. There is a medical need for medication that can speed healing after descemetorhexis and that can help establish a high, functional ECD to maintain corneal transparency.

Ripasudil ophthalmic solution 0.4% (K-321) is a Rho-associated protein kinase (ROCK) inhibitor that has been marketed in Japan since December 2014 as Glanatec[®], with twice daily (BID) dosing for glaucoma and ocular hypertension. Studies in endothelial cells have indicated that K-321 can lead to reduction of apoptosis, enhancement of cell proliferation, and increased rates of migration, all of which may support endothelial healing (Kowa Company Ltd 2019). Moloney et al (2017) first reported use of a ROCK inhibitor to promote healing in patients with FECD treated with Descemet stripping only (DSO). More recently, Macsai et al (2019) reported results from a small study of 18 patients with FECD and central confluent guttae of up to 5 mm diameter who underwent DSO and were subsequently treated with either ripasudil ophthalmic solution 0.4% four times daily (QID) or no ripasudil for 2 months. Overall, patients who underwent DSO with ripasudil recovered vision more quickly [REDACTED]

[REDACTED] The patients in the no-ripasudil group had [REDACTED] while in the ripasudil group there was [REDACTED]. In the short-term studies (8 weeks duration and less) for the development of Glanatec, there were [REDACTED]

[REDACTED]
[REDACTED]
[REDACTED] (Kowa Company Ltd 2019).

Kowa proposes to pursue development of K-321 (ripasudil ophthalmic solution) for the following indication: “the treatment of Fuchs endothelial corneal dystrophy after descemetorhexis.” This will be the first Kowa-sponsored study in patients for this indication.

2 Study Objectives

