5.1 Method of Assigning Patients to Treatment Groups

After confirmation that the study eye descemeterhexis satisfied inclusion criterion 5 (Section 4.1.1) and any pregnancy test is negative (exclusion criterion 1, Section 4.1.2), patients will be randomly assigned at Visit 2 to either placebo, K-321 BID, or K-321 QID treatment (Section 5.2) using a 1:1:1 allocation ratio. An interactive web response system (IWRS) will be used to administer the randomisation schedule. An independent [REDACTED] biostatistician will generate the randomisation schedules using SAS software Version 9.4 (SAS Institute Inc, Cary, North Carolina) or later. The IWRS will link sequential patient randomisation numbers to treatment codes. The randomisation schedule will use an appropriate block size, which will not be revealed other than to the [REDACTED] and Kowa biostatisticians.

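### Does the 34% of eyes that never cleared in the protocol's background contradict the 10% unmeasurable rate in the power simulation?

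*Protocol*

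**What the plan says.** Protocol Section 7.4 sets the size of the trial: "A sample size of 20 patients in each group will be needed". The test behind that number is described as "using a Wilcoxon rank sum test with a 0.050 two-sided significance level with closed testing procedures". The effect it is sized for has its value blacked out: "detect a difference of [REDACTED] in the measurement in the corneal ECD at Week 12". Power is stated separately for the QID and BID comparisons, and both values are redacted. The sample size came from simulation with normally distributed ECD in each arm. The means and SDs are blacked out, and three published series are cited for the simulation.

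Two further inputs are given. The proportions of Week 12 values unmeasurable through oedema and lost through withdrawal "were assumed to be about 10% and about 5%, respectively". In the simulation, "unmeasurable value of Week 12 due to corneal oedema were imputed as zero", and withdrawals were carried forward. The text does not say whether the 10% applies to each arm or is an average, and attaches no source to it directly.

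The Introduction (Section 1) summarises pooled cases of descemetorhexis without grafting: "31 (65%) out of 47 cases eventually achieved a clear cornea". It adds that healing could be seen as early as one month and that oedema still present at six months was unlikely to resolve. It gives no rate at Week 12.

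**The concern.** If 31 of 47 eyes eventually cleared, 16 of 47 did not. If clearance lasts once achieved, the share not clear at Week 12 cannot be smaller than the share that never clears. Set beside that, 10% looks optimistic by a factor of about three. A drug meant to speed healing should also lower the rate relative to placebo, yet the protocol gives a single figure.

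The input matters because zeros are tied at the lowest ranks in the Wilcoxon test. With 20 patients per arm, 10% means 2 zeros per arm and 34% means about 7 (0.34 × 20 = 6.8). If the true rate were near 34% in every arm, the trial would have far less power than planned, and a negative result might be read as better evidence of no effect than it is.

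**Working it through.** **The background rate.** 31/47 = 66.0%, so the printed 65% is a small rounding slip. The complement is 16/47 = 34.0%, exact 95% CI 20.9% to 49.3%. If the true non-clearing rate were 10%, the probability of 16 or more in 47 would be about 0.000007. The two figures therefore could not both be right if they measured the same thing.

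**Do they measure the same thing?** Other sections keep the two apart:

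- Protocol 6.2.3 has the investigator grade oedema as present or absent by corneal layer.
- Protocol 7.5 treats inability to perform ECD because of oedema as a separate assessment outcome.
- SAP addendum Section 2 lists visits with observed oedema and visits where ECD could not be done because of oedema as two categories, so ECD may be readable in some oedematous eyes.
- Protocol 7.2 defines clearance by thickness as well as oedema, so under the trial's own definition an eye without oedema can still fail to clear.

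The 34% is therefore not a lower bound for the simulated input.

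**Planned power.** It cannot be reproduced, because the difference, means, SDs and both powers are redacted.

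**Sensitivity.** The check used these inputs:

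- From the protocol: n = 20 per arm, two-sided alpha 0.05, Wilcoxon rank sum test, ordered two-step testing, oedema values set to zero, 5% withdrawals.
- Assumed: a standardised shift d, chosen so that 10% zeros in both arms gives 80% Step 1 power (d about 1.23) or 90% (d about 1.45). Withdrawn patients take a value from their own arm's distribution. Both active arms share the same d and zero rate.

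The statistic is the normal approximation with tie and continuity corrections:

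z = (|U − n²/2| − 0.5) / √{(n²/12)[(2n + 1) − Σ(t³ − t)/(2n(2n − 1))]}

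Here n²/2 = 200 and t is the size of each tied group. Step 2 counts as a success only if Step 1 is also significant.

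| Zeros, placebo / active | Step 1 / Step 2 power, d ≈ 1.23 | Step 1 / Step 2 power, d ≈ 1.45 |
|---|---|---|
| 10% / 10% | 80% / 67% | 90% / 82% |
| 20% / 20% | 58% / 37% | 70% / 51% |
| 34% / 34% | 31% / 13% | 39% / 18% |
| 34% / 25% | 59% / 39% | 68% / 49% |
| 34% / 20% | 75% / 59% | 83% / 70% |
| 34% / 10% | 95% / 91% | 98% / 96% |

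At d = 1.0 the Step 1 pattern is the same: 65% at 10%/10%, 24% at 34%/34% and 89% at 34%/10%. Moving the placebo mean from 6 SD to 2.5 SD above zero changed the calibrated results by about 1 point or less.

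**Reading the table.** Zeros common to both arms dilute the comparison and lower power. Extra zeros on placebo alone are low ranks in the control arm and raise it. With placebo at 34%, Step 1 power matches the 80% calibration at an active rate somewhere between 10% and 20%. The steepest losses need 34% in both arms, meaning a drug with no effect on whether ECD can be measured, which is at odds with the argument that the drug should lower that rate.

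**The case for a change.** The strongest reply is that the difference between non-clearance and unmeasurable ECD shrinks the problem without removing it. If only half of the never-cleared eyes were unmeasurable, the rate would be 17%. In a simpler run without withdrawals, 17% in both arms cuts Step 1 power from 79% to 64% at a shift of 1.2 SD, and from 88% to 74% at 1.4 SD. The eligibility limits could explain a lower rate than the background: Section 4.1.1 caps the stripped diameter, and Section 4.1.2 excludes remaining confluent guttae, advanced stromal oedema and central thickness of 670 µm or more. Section 7.4 does not make that argument, however. Nor do its listed inputs cover rescue keratoplasty before Week 12, which Section 5.8.2 allows.

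Part of this stands. The 10% has no source tied to it, its split by arm is not stated, and power depends heavily on it.

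It does not show that the plan is wrong. The 17% case again assumes equal rates in both arms. The Introduction describes the 47 cases as ungrafted and compiled from several papers; it does not say they were free of ROCK inhibitor, and gives no selection criteria for them. The three cited series may also have informed the 10%, which the documents cannot settle. The handling of early rescue in Section 7.7.1 is blacked out, so that point can be taken no further.

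**Conclusion.** No change to the plan follows. The 10% and the 34% are related but different quantities from populations that cannot be matched on the documents. No stated power can be shown wrong, because it is redacted, and the direction of any error depends on the arm-specific rates. Calibrated to 80% at 10%/10%, Step 1 power runs from 31% (34% in both arms) to 95% (34% placebo, 10% active). These figures rest on the assumed shift, normal ECD values and the simple treatment of withdrawals.

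A different planning rate would alter neither the test, the alpha, the endpoint nor, on this concern's own terms, the sample size. The Wilcoxon comparison holds its error rate under the null whatever the share of zeros (a null check in the simpler runs gave 0.048), and the ordered procedure in Section 7.7 still applies. The risk of over-reading a negative result is met by Section 7.7.1, which requires the Hodges-Lehmann shift with its Moses 95% interval; that interval reflects the zeros that actually occur. The SAP addendum was also written after the Week 12 unmasking, when a restated planning power would add little to interpretation. A sentence giving the source of the 10% would have made Section 7.4 easier to follow, but its absence is a gap in justification and affects neither analysis nor conduct.

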7.5 Analysis Sets

The following analysis sets will be used in the statistical analyses.

Full-analysis set (FAS): The FAS will consist of all participants who have a successful descemetorhexis procedure performed, were randomly assigned to receive double-mask study drug, received at least one dose of study drug in the study eye, and have at least one assessment of central corneal ECD performed after the descemetorhexis procedure on the study eye. (An assessment of “cannot perform due to corneal oedema” is considered a valid assessment for inclusion in the FAS.) All analyses using the FAS will group participants according to randomised treatment.

Per-protocol set (PPS): The PPS will consist of all FAS participants who complete the 12-week dosing treatment period for the study eye (for the primary analysis only), have at least 80% compliance with study treatment for the study eye, have not taken any prohibited medication, and have no major protocol deviations. Patients who receive rescue therapy will be considered to have completed study treatment for inclusion in the PPS. All analyses using the PPS will group participants according to treatment actually received.

Safety set (SFS): The safety set will consist of all participants who received any study drug. All analyses using the safety set will group participants according to treatment actually received.

The FAS will be the primary analysis set for efficacy analyses. Selected efficacy analyses will be repeated for the PPS. Safety will be summarised using the SFS.

7.6 Description of Subgroups to be Analysed

Due to the small sample size, no subgroup analyses are planned.

7.7 Statistical Analysis Methodology

Statistical analysis will be performed using SAS software Version 9.4 or later. Continuous variables will be summarised using the mean, the SD, median, minimum value, and maximum value. Categorical variables will be summarised using frequency counts and percentages. Unless otherwise noted, the denominator to determine the percentage of participants in each category will be based on the number of participants with available data. Selected ordinal data may be summarised using both descriptive statistics and counts and percentages of participants in each category, as appropriate. Data will be listed in data listings.

Details of the statistical analyses, methods, and data conventions are described in the statistical analysis plan (SAP).

All statistical tests will be 2-sided and performed using a 0.05 significance level, leading to 95% (2-sided) CIs.

A closed 2-step ordered testing procedure will be used to control overall type I error for the primary efficacy endpoint, central corneal ECD at Week 12. In step 1, the K-321 0.4% QID group will be statistically compared with the placebo group. If the step 1 comparison is significant, step 2 will be performed to statistically compare K-321 0.4% BID group with the placebo group. If the statistical comparison made during step 1 is not significant, testing will still be performed to compare the BID group to placebo; however, all p values will be considered nominal/descriptive only.

No other measures will be taken to control error for the multiple secondary and exploratory endpoints or multiple treatment comparisons.

7.7.1 Analysis of Primary Efficacy Endpoint

The primary analysis of central corneal ECD will be performed on the study eye within the FAS via a Wilcoxon rank sum test and will be based on assessments performed by specular microscopy. Testing will be performed in a pairwise manner with each dosing regimen (QID and BID) of K-321 0.4% compared to placebo. For each dosing regimen, the following 2-sided hypothesis will be tested

$H_0: \Delta = 0$ versus $H_a: \Delta \neq 0$

where Δ is the shift in location in central corneal ECDs between the active and placebo groups being compared: ie,

$X_i = e_i$ for $i = 1$ to n for the placebo patients

$Y_j = e_j + \Delta$ for $j = 1$ to m for the K-321 patients

The Hodges-Lehmann estimate (Hodges and Lehmann 1963) for the shift in location (eg, the median of all differences $d=Y_j - X_i$) and Moses 95% CI (Moses 1965) will also be presented.

Week 12 assessments that are unable to be performed due to corneal oedema will be [REDACTED]
[REDACTED]
[REDACTED].

Week 12 assessments that are [REDACTED] due to patient withdrawal or missed visit will be [REDACTED]. Patients who receive a rescue keratoplasty performed prior to Week 12 will be [REDACTED]
[REDACTED]
[REDACTED]
[REDACTED]
[REDACTED]

Sensitivity analyses will be performed by repeating the above analysis and [REDACTED] [REDACTED] for the PPS. The primary analysis methods will also be repeated for the FAS using [REDACTED]
[REDACTED] Additionally, analyses will be performed using assessments performed by HRT for the subset of patients for which the assessments are available.

